10.6 Safety Analyses

10.6.1 Adverse Events and Disease-Related events

The Medical Dictionary for Regulatory Activities (MedDRA) version 19.0 or later will be used to code all events categorized as adverse events (AEs) or disease-related events (DREs) to a system organ class and a preferred term. Severity of AEs will be graded using the CTCAE ([Appendix B](#)) and recorded on the eCRF. All adverse event tables will

be summarized by actual treatment group. Treatment-emergent adverse events are events with an onset after the administration of the first dose of IP as defined in [Section 6.3](#).

Subject incidence of all treatment-emergent AEs, serious AEs, AEs leading to withdrawal of investigational product, and fatal AEs will be tabulated by system organ class and preferred term in descending order of frequency.

Summaries of treatment-emergent and serious AEs occurring in at least 1% of the subjects by preferred term in any treatment arm will be provided in descending order of frequency.

Subject incidence of DREs will be summarized by system organ class and preferred term for all treatment-emergent DREs and fatal DREs.

Subject incidence of adverse events related to a device will be tabulated by preferred term in descending order of frequency by treatment group.

Subject incidence of adverse events associated with lipid lowering therapies:

- Muscle-related
- Liver-related

associated with injectable protein therapies:

- Injection site reactions
- Hypersensitivity or allergic reactions

and potential hepatitis C infections will be summarized by category and preferred term.

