## **9. SAFETY DATA COLLECTION, RECORDING, AND REPORTING**

### **9.1 Definition of Safety Events**

#### **9.1.1 Disease-related Events**

Disease-related events are events (serious or non-serious) anticipated to occur in the study population due to the underlying disease. In this study, subjects are at risk or are known to have cardiovascular disease. Therefore, disease-related events potentially include manifestations and complications of atherosclerotic vascular disease such as coronary artery disease, angina, myocardial infarction, ischemic stroke, transient ischemic attack, carotid artery disease, peripheral vascular disease, and testing suggesting progression of atherosclerotic vascular disease. Such events do not meet the definition of an adverse event unless assessed to be more severe than expected for the subject's condition.

Disease-related events and/or disease-related outcomes that do not qualify as serious adverse events:

- An event which is part of the normal course of disease under study, **with no causal relationship with IP/protocol-required therapies** (eg, disease progression or

hospitalization due to disease progression) is to be reported as a disease-related event.

- Death is due to the disease under study; the event is to be recorded on the Event CRF as a disease-related event.

If the outcome of the underlying disease is worse than that which would normally be expected for the subject, or if the investigator believes there is a causal relationship between the IP/study treatment protocol-required therapies and disease worsening, the event must be reported as an adverse event or serious adverse event.

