#### 9.1.4 Serious Adverse Events

A serious adverse event is defined as an adverse event that meets at least 1 of the following serious criteria (unless it meets the definition of a disease-related event as defined in [Section 9.1.1](#)):

- fatal
- life threatening (places the subject at immediate risk of death)
- requires in-patient hospitalization or prolongation of existing hospitalization
- results in persistent or significant disability/incapacity
- congenital anomaly/birth defect
- other medically important serious event

A disease-related event as described above is to be reported as a serious adverse event if:

- the event meets at least 1 of the serious criteria above, **AND**
- the subject's pre-existing condition becomes worse than what the investigator would consider typical for a patient with the same underlying condition, **OR**
- the investigator believes a causal relationship exists between the IP/protocol-required therapies and the event

An adverse event would meet the criterion of "requires hospitalization", if the event necessitated an admission to a health care facility (eg, overnight stay).

If an investigator considers an event to be clinically important, but it does not meet any of the serious criteria, the event could be classified as a serious adverse event under the criterion of "other medically important serious event". Examples of such events could include allergic bronchospasm, convulsions, blood dyscrasias, DILI (see [Appendix A](#) for DILI reporting criteria), or events that necessitate an emergency room visit, outpatient surgery, or urgent intervention.

If adverse events correspond to grade 4 "life threatening" Common Terminology Criteria for Adverse Events (CTCAE) grading scale criteria (eg, laboratory abnormality reported as Grade 4 without manifestation of life threatening status), it will be left to the investigator's judgment to also report these abnormalities as serious adverse events. For any adverse event that applies to this situation, comprehensive documentation of the event's severity status must be recorded in the subject's medical record.

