## 9.2 Safety Event Reporting Procedures

### 9.2.1 Disease-related Events

The investigator is responsible for ensuring that all disease-related events observed by the investigator or reported by the subject that occur from the time of randomization through the EOS/safety follow-up visit are reported using the Event CRF. Additionally, the investigator is required to report a fatal disease-related event on the Event CRF.

Events assessed by the investigator to be related to the IP/study treatment/protocol-required therapies, and determined to be serious, require reporting of the event on the Event CRF.

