4.1.3 Safety Endpoints

- subject incidence of treatment emergent adverse events
- safety laboratory values and vital signs at each scheduled assessment

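### Serious non-fatal disease-related events, and disease-related events that lead to IP withdrawal, cannot be identified as such in any planned safety table

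*SAP*

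**What the plan says.** Protocol 9.1.1 defines disease-related events as anticipated manifestations and complications of atherosclerotic vascular disease, whether serious or not. Its examples run from myocardial infarction, ischaemic stroke and transient ischaemic attack to test results that suggest progression. It then says: "Such events do not meet the definition of an adverse event unless assessed to be more severe than expected". An event thought to be caused by treatment also returns to the AE or SAE category.

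Protocol 9.1.4 defines an SAE as an adverse event meeting a serious criterion, "unless it meets the definition of a disease-related event". It gives a way back. "A disease-related event as described above is to be reported as a serious adverse event if" it meets a serious criterion and is either worse than the investigator considers typical or, in the protocol's words, "the investigator believes a causal relationship exists between the IP/protocol-required therapies and the event".

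Protocol 9.2.1 requires collection of all DREs that "occur from the time of randomization through the EOS/safety follow-up visit are reported using the Event CRF".

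SAP 4.1.3 sets the event-based safety endpoint as "subject incidence of treatment emergent adverse events". SAP 6.3 builds TEAEs from events categorised as AEs, defines SAEs as the serious subset of TEAEs, and makes treatment-emergent DREs a separate category.

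SAP 10.6.1 plans subject-incidence tables for all TEAEs, serious AEs, AEs leading to IP withdrawal and fatal AEs. For the other category it says: "Subject incidence of DREs will be summarized by system organ class and preferred term for all treatment-emergent DREs and fatal DREs". Protocol 10.5.4 plans the same two DRE tables.

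**The concern.** The safety objective is to compare safety and tolerability in people with type 2 diabetes. Inclusion criterion 104 admits subjects with prior infarction, angina, stroke, TIA, revascularisation or peripheral arterial disease, and exclusion criterion 201 removes only those with recent events. Serious atherosclerotic events during the 12 weeks are therefore plausible.

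A reader of the study report will look to the serious-event and withdrawal tables for the number of subjects with a serious event and the number who stopped IP because of an event. Those tables are limited to AEs. Whether an infarction enters them depends on the investigator's view of what is typical for that patient, at any of about 80 sites. What is at stake is whether the total subject incidence of serious events, and of events leading to withdrawal, can be read from the planned output at all.

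**Working it through.** The plan states no figure to reproduce on this point. The check is to trace where an event goes under the definitions.

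**Step 1. Placement.** Take a treatment-emergent, non-fatal atherosclerotic event that meets a serious criterion and is followed by stopping IP.

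| Planned table | Judged worse than typical, or caused by treatment (AE/SAE) | Judged typical and unrelated (DRE) |
|---|---|---|
| All TEAEs | counted | not counted |
| Serious AEs | counted | not counted: SAP 6.3 makes SAEs a subset of TEAEs |
| AEs leading to IP withdrawal | counted | not counted |
| All treatment-emergent DREs | not counted | counted, with no split by seriousness or withdrawal |
| Fatal DREs | not counted | not counted |
| Disposition, SAP 10.2 | counted as an IP discontinuation, with reason | counted as an IP discontinuation, with reason |

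**Step 2. Can the missing subsets be recovered?**
- The all-DRE table mixes serious and non-serious events. A reader may guess that an infarction was serious, but cannot do so for angina, and cannot derive the number of subjects with at least one serious event across terms.
- The disposition table gives reasons for stopping, not event terms. The reasons in protocol 8.3.1 are broad, such as a safety concern.
- Adding the AE and DRE tables does not work, because one subject can be in both.

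**Step 3. Effect of the split on a threshold.** SAP 10.6.1 also summarises AEs by preferred term when they reach 1% in any arm. Suppose, in a placebo arm of about 130, one subject has unstable angina recorded as an AE and another has it recorded as a DRE, with the evolocumab arm below 1%. The AE summary sees 1/130 = 0.8% and omits the term. Combined, it is 2/130 = 1.5%, above the threshold.

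**Step 4. Scale, on assumed rates only.** Inputs: arm sizes of about 270 and 130 (SAP 3.1), and an assumed proportion r of subjects with a serious non-fatal DRE not upgraded to an SAE. The expected number is n × r, and the chance of at least one such subject is 1 − (1 − r)^n.

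| Assumed r | Expected, evolocumab | Expected, placebo | Chance of at least one, evolocumab | Chance of at least one, placebo |
|---|---|---|---|---|
| 0.5% | 1.35 | 0.65 | 74% | 48% |
| 1% | 2.7 | 1.3 | 93% | 73% |
| 2% | 5.4 | 2.6 | 99.6% | 93% |
| 3% | 8.1 | 3.9 | about 100% | 98% |

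**Step 5. Share of serious-event subjects missed.** With d subjects having such a DRE and s having an SAE, and no overlap, the share is d/(d + s). In 400 subjects, DRE 0.5% and SAE 6% give 2/(2 + 24) = 8%. DRE 2% and SAE 1% give 8/(8 + 4) = 67%. The answer is set by the two assumed rates.

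**The case against.** The strongest reply is that nothing is lost. Every treatment-emergent DRE is tabulated by system organ class and preferred term, fatal DREs have their own table, and what is missing is a breakdown. Events suspected to be caused by treatment, or worse than typical, return to the AE and SAE tables. The tables in question are labelled as AE tables, the SAP matches protocol 10.5.4, safety is descriptive, and no test is affected. Protocol 10.5.4 also allows subject-level data in place of tables when incidence is low.

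Much of this stands, and it rules out stronger readings that a reader might infer:

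- That these events are under-counted in every safety table. They are not: the all-DRE table includes them, and laboratory, vital-sign and exposure summaries are unaffected.
- That the discontinuation rate is too low. It is not: SAP 10.2 summarises all IP discontinuations with reasons.
- That the comparison between arms is biased. Classification is made under double-blind conditions, and nothing in the documents shows that it would differ by arm.
- That a definite share of serious events, such as a quarter or more, is missed. The documents give no rate from which to derive one.
- That the SAP departs from the protocol. Both documents share the gap.

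The reply does not close the gap itself. The subject incidence of serious events and of events leading to withdrawal, across AEs and DREs, cannot be read or rebuilt from the planned tables. The subject-level option is permissive and adds no seriousness or withdrawal subset for DREs.

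**Conclusion.** The point holds as a reporting gap. Atherosclerotic events that the investigator considers typical and unrelated to treatment fall outside the TEAE and SAE counts, and only all and fatal DREs are tabulated. Serious non-fatal DREs and DREs leading to IP withdrawal therefore appear in the all-DRE table without being identifiable as such. The serious-AE and AE-leading-to-withdrawal tables understate the total subject incidence of serious events and of events leading to withdrawal by however many subjects have only such a DRE.

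The size is unknown. At an assumed rate of 0.5% to 1%, a handful of subjects is involved, and at least one in the evolocumab arm is likely (74% to 93%). The effect is on absolute rates in a descriptive safety summary, not on any hypothesis test. The gap is worth closing because it changes a reported safety result at little cost.

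**What to change.** In SAP 10.6.1, by actual treatment group:

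1. Add subject incidence of treatment-emergent serious DREs by system organ class and preferred term.
2. Add the same for DREs leading to IP withdrawal, if the Event CRF records action taken for DREs.
3. Add combined AE-or-DRE tables for all, serious, leading-to-IP-withdrawal and fatal events, counting each subject once per preferred term.
4. Keep the existing separate AE and DRE tables.

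Before doing so, confirm what the CRF holds. Protocol 9.1.1 recognises serious and non-serious DREs, and protocol 9.2.1 puts them on the Event CRF. However, protocol 9.2.2.1 lists action taken as a required attribute for adverse events, and neither document says that seriousness or action taken is recorded for DREs. If both are recorded, no new data are needed.

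The cost is a few more tables and a slightly less favourable reported serious-event rate.

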10.6.2 Laboratory Test Results

Descriptive statistics will be provided for actual values and changes from baseline in select laboratory parameters at each protocol-specified scheduled visit. Laboratory analytes are provided in the protocol [Table 2](#). Lab shift tables using the CTCAE v4.03 or later grading will be used for the select analytes of interest, when applicable.

In addition, CK and liver function test (LFT) abnormalities will be assessed by the incidence overall and by visits of the following categories:

- CK > 5 x ULN
- CK > 10 x ULN
- ALT or AST \geq 3 x ULN
- ALT or AST \geq 5 x ULN

- Total bilirubin $\geq 2 \times$ ULN
- (ALT or AST $\geq 3 \times$ ULN) and (Total bilirubin $\geq 2 \times$ ULN and ALP $< 2 \times$ ULN)

10.6.3 Vital Signs

Systolic and diastolic blood pressures and heart rate will be summarized for each treatment group using descriptive statistics at each scheduled visit.

10.6.4 Exposure to Investigational Product

Descriptive statistics will be produced to describe the patient-month exposure to investigational product and the categorical representation of dose received.

Exposure definitions are provided in [Section 6.3](#).

10.6.5 Exposure to Other Protocol-specified Treatment

The number and proportion of subjects receiving selected lipid regulating medications captured on the Lipid Regulating Concomitant Medications eCRF will be summarized by treatment group. Summaries will be provided for baseline use and use after Study Day 1. The subject incidence of changes in lipid regulating medications during the treatment period will also be provided by treatment group.

10.6.6 Exposure to Concomitant Medication

The number and proportion of subjects receiving the diabetes related medications of interest will be summarized by category and preferred term for each treatment group as coded by the World Health Organization Drug (WHODRUG) dictionary. The subject incidence of changes in diabetes related medications, including the reason for change, during the treatment period will also be provided by treatment group.

11. Changes From Protocol-specified Analyses

There are no changes to the protocol-specified analyses.

12. Literature Citations / References

The Task Force for the management of dyslipidaemias of the European Society of Cardiology (ESC) and the European Atherosclerosis Society (EAS). ESC/EAS Guidelines for the management of dyslipidaemias. European Heart Journal. 2011; 32:1769–1818.

Hochberg Y. A sharper Bonferroni procedure for multiple tests of significance. *Biometrika* 1988;75:800-802.

Wiens BL. A fixed sequence Bonferroni procedure for testing multiple endpoints. *Pharmaceut. Statist.* 2003; 2:211-215.

13. Appendices

Appendix A. Analytical Study Week Assignments

Selected endpoints will be summarized by scheduled study visits in descriptive analyses. Since the actual visits may not exactly coincide with their scheduled visit day, the actual visit day is mapped to the study visit generally by non-overlapping consecutive intervals covering the entire time continuum. The mapping intervals for all distinct schedules are summarized in the following table:

Analytical Study Week	Week 8	Week 10	Week 12
Scheduled Visit Day	57	71	85
Chemistry, HbA1c, Urinalysis, Body Weight, Waist circumference, MMTT parameters,			>1
Vital Signs	(1, 63]	(63, 77]	(77, 91]
Fasting Lipids, ApoA1, ApoB, Lp(a), PCSK9,		(1, 77]	(77, 91]

Handling multiple records assigned to an analytical study week:

If there is more than one record in a study week interval, the analytical record for that specific study week will be defined as the record closest to the scheduled visit day of that specific study week ($7 \times$ study week + 1). If two records are equidistant from the scheduled day, then the earlier record will be chosen. If there are multiple records on the same day, the last record will be used.

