#### **7.2.3 Double-blind Treatment Period**

Visits will occur per the Schedule of Assessments ([Table 1](#)) during the treatment period from day 1 through week 12. Visits during the treatment period must be completed within  $\pm$  3 days of the target visit date. For visits with IP administration at the study site, administration should be the last procedure to be performed during each visit.

Evolocumab/placebo is to be self-administered in an appropriate non-clinic setting (eg, at home) at week **4  $\pm$  3 days**. Subjects who do not wish to self-inject at home may return to clinic for injection. Observed, in-clinic dosing should occur at day 1 and at week **8  $\pm$  3 days**.

If a subject withdraws from the study early, all efforts should be made to complete and report the observations as thoroughly as possible up to the date of withdrawal. The procedures for the EOS visit should be completed at the time of withdrawal ([Section 7.2.4](#)).

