10.5.3 Analyses of Exploratory Endpoints

Exploratory endpoints related to lipid parameters and PCSK9 will be summarized by randomized treatment group and by scheduled visit using descriptive statistics.

HbA1c and FBG will be summarized at each scheduled assessment by actual treatment group.

Area under the curve (AUC) and incremental AUC will be calculated for laboratory parameters collected for the MMTT at day 1 and at week 12. Change and percent change from day 1 to week 12 in AUC and incremental AUC will be provided by actual treatment group. Analysis will be performed separately for those subjects who have the extended timepoint assessments.

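### SAP Appendix A reports an early-withdrawal HbA1c, chemistry or MMTT value as week 12 whenever the subject has no record nearer day 85

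*SAP*

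**What the plan says.** SAP Appendix A assigns records to study weeks by study day. For the row "Chemistry, HbA1c, Urinalysis, Body Weight, Waist circumference, MMTT parameters", the week 8 and week 10 cells are empty and the week 12 cell reads > 1. Vital signs and fasting lipids have a week 12 window of (77, 91]. The appendix states its general aim: "the actual visit day is mapped to the study visit generally by non-overlapping consecutive intervals covering the entire time continuum".

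Where several records fall in one window, "the analytical record for that specific study week will be defined as the record closest to the scheduled visit day of that specific study week". On ties, "If two records are equidistant from the scheduled day, then the earlier record will be chosen".

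Protocol 7.2.3 says of subjects who leave the study early: "The procedures for the EOS visit should be completed at the time of withdrawal". Protocol Table 1 includes chemistry, HbA1c and the MMTT in the week 12/EOS visit.

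SAP 10.5.3 then uses the label. For glycaemia, "HbA1c and FBG will be summarized at each scheduled assessment by actual treatment group". For the meal test it reports "Change and percent change from day 1 to week 12 in AUC and incremental AUC". SAP 10.6.2 summarises laboratory values at each scheduled visit, and CK and liver abnormalities both overall and by visit. Neither document excludes early-termination or unscheduled records from these summaries.

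**The concern.** A result labelled week 12 should describe subjects after about 12 weeks. Under this window, a subject who leaves on day 15 supplies a week 12 HbA1c, fasting glucose and MMTT after two weeks on study. This does not match the MMTT endpoint, which SAP 4.1.4 and 10.5.3 define as change from day 1 to week 12. It also sits awkwardly with SAP 10.1, which says missing safety data are not imputed: using an early chemistry value where no week 12 value exists acts much like carrying an observation forward, without saying so.

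HbA1c, fasting glucose and the MMTT are the diabetes-specific results in a trial whose population is defined by diabetes. A reader of these tables could not tell how many of the week 12 values were taken much earlier.

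**Working it through.** **Target day.** Appendix A's formula is 7 × study week + 1. For weeks 8, 10 and 12 it gives 57, 71 and 85, matching the table. For the protocol's visit window ("Visits during the treatment period must be completed within" 3 days of target), the week 12 visit runs from day 82 to day 88.

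**Applying the rule.** Take the record closest to day 85 within the window, and the earlier one on a tie:

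| Records after day 1 | Week 12 value under > 1 | Week 12 value under > 77 |
|---|---|---|
| Day 15 (withdrawal) | Day 15 | None |
| Day 60 (withdrawal) | Day 60 | None |
| Day 30 (unscheduled, no week 12 visit) | Day 30 | None |
| Days 20 and 85 | Day 85 | Day 85 |
| Days 60 and 88 | Day 88 (distance 3 against 25) | Day 88 |
| Day 120 | Day 120 | Day 120 |

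The first three rows show the problem. The fourth and fifth show that a subject with a real week 12 visit is handled correctly.

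**Ceiling on numbers.** SAP 3.2 plans 400 subjects, with dropout of 5% (triglyceride and HDL-C power) or 10% (LDL-C power). If every dropout had an end-of-study assessment:

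- 5%: 400 × 0.05 = 20 subjects (270 × 0.05 = 13.5 evolocumab, 130 × 0.05 = 6.5 placebo)
- 10%: 400 × 0.10 = 40 subjects (27 evolocumab, 13 placebo)

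**Effect on the mean.** Let d be the share of subjects with an early value, and q the fraction of the week 12 change that those values carry. The reported mean change, relative to its full size, is 1 − d(1 − q):

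| d | q = 0 | q = 0.5 |
|---|---|---|
| 0.05 | 0.95 | 0.975 |
| 0.10 | 0.90 | 0.95 |

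Suppose instead that withdrawals are uniform over days 2 to 77 (mean day 39.5) and change accrues linearly. Then q = 39.5/85 = 0.465, and the shrinkage is 0.05 × 0.535 = 2.7% or 0.10 × 0.535 = 5.4%. The values of q and the withdrawal pattern are assumptions; the documents give neither. If q exceeds 1, as when subjects leave because they are deteriorating, the expression exceeds 1 and the mean is enlarged.

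**The case against.** The window looks deliberate. These parameters have one planned assessment after day 1, and an appendix that aims to cover the whole time line arrives naturally at > 1. That explains having a single column, but not calling a day 15 value week 12.

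Four stronger readings are tempting, and the documents do not support them.

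- A reader might infer that unscheduled values enter the week 12 results generally. They do not: the closest-record rule drops them for anyone with a record nearer day 85. They count only when there is none, for example when repeat liver tests under Protocol Appendix A are in the analysis data and the subject never attends week 12.
- A reader might infer that the treatment comparison is biased, or that the error is anti-conservative for glycaemic safety. SAP 10.5.3 and 10.6.2 plan descriptive summaries here, outside the multiplicity scheme, and the co-primary LDL-C endpoints are not in this row. Shrinkage toward zero needs early values to show less change, which fails if subjects leave because of glycaemic deterioration.
- A reader might take 20 to 40 subjects as the expected number. It is a ceiling. Protocol 8.1 treats withdrawal of consent as ending further procedures, and death or loss to follow-up usually gives no final assessment. Under Protocol 6.2.2, subjects who only stop investigational product keep attending and can supply a true week 12 value.
- A reader might treat (77, 91] for vital signs as the SAP's own standard for excluding early data. The same row maps days after 1 up to 63 to week 8, so its lower limit only divides time among three visits.

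**Conclusion.** The point stands as a labelling fault with a small effect. As written, the SAP reports early-withdrawal values as week 12 in the HbA1c, fasting glucose, MMTT AUC and by-visit laboratory summaries when no nearer record exists, and does the same with unscheduled values in such subjects. At most 20 to 40 of 400 subjects are affected at the planning dropout, and probably fewer.

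Under the assumed range for q of 0 to 0.5, mean change at the ceiling is 90% to 97.5% of its full size; the direction cannot be settled from the documents. No confirmatory result depends on this row, and the overall CK and liver incidence is unaffected because it does not use the window. The change is worth making because the rule puts a wrong label on data and costs almost nothing to correct.

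**What to change.** In SAP Appendix A, change the week 12 window for this row from > 1 to > 77, with no upper limit. Copying (77, 91] would be a mistake: Protocol section 7 foresees visits outside their windows, and 7.2 allows fasting repeats to fall outside them, so a genuine week 12 visit on day 92 or later would be lost.

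Summarise records from days 2 to 77 in a separate row labelled early termination/unscheduled. The alternative is to keep > 1, relabel the column as the last post-baseline value, and add an observed week 12 summary. Either way, keep every post-baseline record in the overall CK and liver incidence, as SAP 10.6.2 already provides.

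With the > 77 window, the cost is one edited table row, one added summary row, and slightly fewer subjects in the week 12 summaries. Those summaries then lie closer to completers only, so the early-termination row should be read beside them.
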